### 6.6.3 Study Completion

A study completion form must be completed for all subjects:

- In whom mortality has been documented
- Who voluntarily withdraw from the study or are withdrawn by the investigator to protect subject rights, welfare, or well-being (§6.6.1)
- Who are lost to follow-up and administratively withdrawn from the study (§6.6.2)
- Who have completed the final protocol-specified follow-up assessment:
  - The final protocol-specified assessment for patients who leave the index procedure catheterization laboratory with an implanted CLAAS device is the 12-month visit (§7.8).

## 6.7 Protocol Deviations

All deviations from the requirements of this Clinical Investigation Plan will be considered protocol deviations. In the event that a subject-level protocol deviation is identified by the site, a Protocol Deviation form should be completed in the eCRF and submitted to the Sponsor. Protocol deviations that will be collected include:

- Failure to obtain informed consent, or failure to obtain informed consent prior to the performance of study-specific procedures or assessments
- Enrollment of a subject who did not meet all study inclusion criteria, or who met one or more study exclusion criteria
- Failure to complete protocol-specified assessments, or completion of protocol-specified assessments outside of the protocol-defined time frame

It is the Site Principal Investigator's responsibility to ensure that there are no deviations from the protocol and to maintain compliance with all established procedures of the applicable EC. If a deviation from the protocol is deemed necessary by the Investigator to protect the safety or physical well-being of a subject, the Investigator is requested to notify the Sponsor as soon as practicable (if possible, before the deviation has occurred).

## 7.0 Study Procedures and Assessments

### 7.1 Schedule of Procedures and Assessments

Table 3. Study Schedule of Procedures and Assessments

	Screening	Index Procedure (day 0)	Pre-discharge 	7 Days (+2 days) 	45 days (45 ± 7 days)	6 months (± 30 days)	12 months (± 30 days)
	Clinic Visit	Clinic Visit	Clinic Visit	Telephone Contact / Optional Clinic Visit	Clinic Visit	Clinic Visit	Clinic Visit
Demographics and Medical History	●						
Review of General Eligibility Criteria	●						
Informed consent	●						
Physical Examination	●		●		●		●
Stroke Assessment	●		●	●	●	●	●
CHA2DS2-VASc; HAS-BLED scores	●						
Pregnancy Test	●						
Laboratory tests	●						
12-lead ECG	●						
Brain Imaging	●		●				
TTE			●				
TEE	● 	● 			●	●	●
ICE		● 					
Angiography		●					
LAA occluder implantation		●					
Concomitant Medications	●	●	●	●	●	●	●
Adverse events	● 	●	●	●	●	●	●

 The pre-discharge visit must be conducted prior to hospital discharge from the index procedure; patients discharged on day 6 or earlier must also be followed up via telephone contact at 7 (+2) days post-procedure. For subjects who have not been discharged before day 7, the 7-day assessment may be performed in the clinic and no separate telephone contact is necessary.

 In patients who have been discharged from the index procedure hospitalization on day 6 or earlier, a telephone contact must be conducted at 7 (+2) days post procedure, and must include ascertainment of

	
survival status, QVSFS, concomitant medication documentation, and reporting of any adverse events that may have occurred since the pre-discharge assessment.
 
The Questionnaire for Verifying Stroke-Free Status (QVSFS) and NIHSS must be completed at baseline and during each clinic visit to screen for interceding signs and symptoms of stroke or TIA. The modified Rankin Scale (mRS) must also be completed at baseline to establish the pre-stroke baseline value. For telephone contacts, stroke screening will consist of the QVSFS only. If a neurologic event is suspected at any time point, a formal neurologic examination and evaluation (to include the mRS) must be performed by a neurologist.
 
 Female subjects of childbearing potential must have a pregnancy test (by site standard method) within 7 days prior to the index procedure to confirm study eligibility criteria.
 
 Laboratory testing should be performed per site standard practice and should include CBC and serum creatinine.
 
 A 12-lead ECG should be performed at baseline and repeated with any signs or symptoms of myocardial ischemia.
 
 Patients with a history of stroke are required to have a baseline MRI (or CT, if MRI is contraindicated) performed within 90 days prior to the scheduled index procedure. Brain imaging need not be repeated if an MRI or CT performed within 90 days pre-procedure as part of the standard of care is available. Patients with history of significant brain trauma or intra-cranial surgery should have a post procedure/event CT or MRI available for review.
 
 An initial evaluation of echocardiographic eligibility based on review of the pre-procedure TTE and/or TEE (or cardiac CT, if that modality is the site standard of care for pre-procedure anatomic assessment) should be performed prior to the index procedure.
 
 TEE (or CT) performed within 90 days prior to consent will be accepted, otherwise TEE must be conducted after consent.
 
TTE performed within 6 months prior to consent will be accepted, otherwise TTE must be conducted after consent.
 
TEE performed after implant delivered, prior to tether release.
 
At time of index procedure, ICE performed to confirm eligibility criteria prior to enrollment.

--	---

## 7.2 Screening

The following tests and examinations must be performed prior to the procedure to verify eligibility and to collect baseline study data. Assessments performed as part of standard medical care prior to study enrollment are valid sources of data for verifying study eligibility and collecting baseline study data, provided that the previously performed assessments comply with applicable protocol requirements.

- Relevant medical history and patient demographic information
- Review of general inclusion, echo criteria and exclusion criteria
- Physical examination, to include NYHA functional class
- Stroke assessment (within 14 days pre-procedure), to include:
  - Questionnaire for Verifying Stroke-Free Status (QVSFS)
  - NIH Stroke Scale (NIHSS); the NIHSS must be performed by a neurologist or NIHSS-certified research staff
  - Modified Rankin Scale (mRS) to establish the pre-stroke baseline value; the mRS must be performed by a neurologist or research staff who have completed mRS training
  - Patients with documented history of stroke, TIA, or in whom an incident neurologic event is suspected on the basis of the QVSFS, NIHSS, or other signs or symptoms,

will require a neurologic examination and evaluation be performed by a neurologist or clinical designee (e.g., neurology fellow)

- Atrial fibrillation stroke risk assessment with the CHA2DS2-VASc scores
- Major bleeding risk assessment with the HAS-BLED score
- Female patients of childbearing potential must have a pregnancy test (by site standard) performed within 7 days prior to the procedure
- Laboratory testing per site standard practice; if laboratory testing is part of the standard of care and includes CBC and serum creatinine, these should be recorded. The results of any additional laboratory tests performed per site standard practice should also be collected.
- A 12-lead electrocardiogram (ECG). An ECG performed within 30 days prior to the procedure may be used as the baseline ECG, provided there have been no signs or symptoms of myocardial ischemia between the time of the ECG and the screening assessment (in which case the ECG should be performed within 24 hours prior to the date of the index procedure).
- Brain imaging. Patients with a history of stroke are required to have a baseline MRI (or CT, if MRI is contraindicated) performed within 90 days prior to the scheduled index procedure. NOTE: Brain imaging need not be repeated if an MRI or CT performed within 90 days pre-procedure as part of the standard of care is available.
- Transthoracic echocardiogram (TTE) or TEE per site standard practice; if TTE and/or TEE (or cardiac CT) is performed as part of the standard of care, it should be reviewed by the investigating physician to evaluate echocardiographic eligibility. Note that echocardiographic eligibility must be confirmed by echocardiography prior to subject enrollment.
- Documentation of all concomitant medications

## 7.3 Index Procedure

### 7.3.1 Pre-Procedure Medical Therapy

Pre-procedure anticoagulation therapy should be managed in accordance with standard institutional practice.

The following should be administered prior to the index procedure:

- ASA 81-100 mg (administered prior to procedure and continued daily)

### 7.3.2 Intraprocedural Medical Therapy

Intraprocedural anticoagulation should be maintained according to physician standard practice in accordance with published guidelines and local standards of care, with a goal of maintaining an activated clotting time (ACT) of 250-350 sec throughout the procedure. The highest and lowest intraprocedural ACT measurements must be recorded in the CRF for all subjects.

All medications administered, including the dose and timing, should be recorded in the patient's medical record and the CRF.

### 7.3.3 Transseptal Puncture

Percutaneous femoral vein access and transseptal puncture should be performed per physician standard practice using a standard commercially-available transseptal access system.

### 7.3.4 Eligibility Confirmation

Prior to implant, the investigator should confirm via echocardiographic imaging that the patient is eligible for participation in the study:

- 1) Confirm that the patient does not meet any echocardiographic exclusion criteria (§6.2.2.2)
- 2) Confirm that LAA anatomy is appropriate for implantation of the CLAAS implant per the device Instructions for Use

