## 1.0 Document Control

### 1.1 Version History

Version (Date)	Description
A (March 22, 2019)	Initial submission to Prague
B (23 April 2021)	Added modified delivery system to Section 4.2. Modifications were made based on learnings from the US Early Feasibility Study and the European First in Human Trial.
	Echocardiographic eligibility is evaluated prior to implant delivery. This has been updated throughout.
	Added option of Cardiac CT scan at 12-M due to potential COVID restrictions.

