#### 4.2.4.2 CLAAS Delivery System

Delivery of the implant is achieved with two coaxial catheters. An access sheath that contains a metal braid, PTFE liner, Pebax, and polyurethane materials is initially placed into the proper position within the LAA. The pre-attached implant is loaded into the distal end of the braided, PTFE lined, polyurethane delivery catheter either by hand or with the assistance of the supplied hydraulic loader.

[figure not shown]
Ver. B – 23 April 2021

CONFIDENTIAL

[figure not shown]
NOTICE: The information contained in this document is CONFIDENTIAL and PROPRIETARY to Conformal Medical, Inc., and may not be disclosed to anyone who is not a recipient or reviewer of this protocol without express prior written consent of Conformal Medical.

The delivery catheter is advanced through the access sheath to the LAA for implant delivery. The catheters are sufficiently long to access the LAA from a right femoral vein puncture. The delivery catheter working length is designed such that when the delivery catheter is locked to the access sheath, its distal tip is about 3cm short of the access sheath tip. This allows the user to advance the implant from the delivery catheter into the access sheath prior to deploying it into the patient.

Each catheter has a hemostatic valve at its proximal end that can be closed to prevent blood loss or opened to pass catheters (Figure 5 and 6).

**Figure 5:** Single curve Access Sheath.

**Figure 6:** Delivery catheter assembly with deployment handle, hemostatic valve, injection ports, and implant loading cone.

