#### 6.2.2.2 Echocardiographic Exclusion Criteria

6.2.2.2.1 Left atrial appendage anatomy cannot accommodate the CLAAS device per manufacturer IFU

6.2.2.2.2 Intracardiac thrombus or dense spontaneous echo contrast, as visualized by echocardiography prior to implant

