6.2.2.2.7 Moderate or severe mitral valve stenosis (mitral valve area <1.5 cm^2)

6.2.2.2.8 Complex atheroma with mobile plaque of the aorta

6.2.2.2.9 Patient has evidence of cardiac tumor

### 6.3 Subject Screening

The study site will maintain a log of all screened and consented subjects. Reasons for meeting study criteria but failing to be enrolled will be captured on the screening log and entered into the database.

Potentially eligible subjects will undergo the process of informed consent (§6.4) prior to the performance of any study-specific assessments.

Potentially eligible subjects will be enrolled in the study only when the CLAAS Access Sheath has been introduced into the patient's body. Patients who do not meet general or echocardiographic eligibility criteria, or in whom the CLAAS Access Sheath is not introduced, will not be enrolled in the study.

Screen failures may be re-enrolled at a future date if it is determined that the eligibility criteria that initially excluded them from participation are no longer applicable (e.g., a thrombus identified on the initial TEE has resolved, a prior stroke is now outside of the exclusion window) or larger device is available.

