## **10.2 Analysis Populations**

### **10.2.1 Intention to Treat (ITT) Analysis Population**

The Intention to Treat (ITT) analysis population is defined as all subjects enrolled in the study (the point of enrollment is introduction of the CLAAS Access Sheath into the patient's body), regardless of the treatment actually received.

The ITT population will be the primary analysis population for the primary safety endpoint, the primary performance endpoint, and all secondary endpoints and other measures.

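### Version B dates the eligibility check inconsistently and does not settle whether a patient found unsuitable after the Access Sheath is in belongs to the ITT population

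*Combined protocol and SAP*

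**What the plan says.** All references are to Version B (23 April 2021) of the combined protocol and SAP.

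**When eligibility is settled**
- Section 7.3.4: "Prior to implant, the investigator should confirm via echocardiographic imaging that the patient is eligible for participation in the study". The check covers the echocardiographic exclusions and the fit of the appendage to the Instructions for Use.
- Exclusion 6.2.2.2.2 (thrombus or dense echo contrast) is likewise dated only to before implant.
- Section 7.2: "Note that echocardiographic eligibility must be confirmed by echocardiography prior to subject enrollment".
- Section 7.1, Table 3, footnote 12: "At time of index procedure, ICE performed to confirm eligibility criteria prior to enrollment".

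**What makes a patient enrolled**
- Section 10.2.1 defines the ITT population as everyone enrolled, whatever treatment followed, and adds that "the point of enrollment is introduction of the CLAAS Access Sheath into" the body.
- Section 6.3: "Patients who do not meet general or echocardiographic eligibility criteria, or in whom the CLAAS Access Sheath is not introduced, will not be enrolled".
- Sections 6.5 and 7.3.6 tie enrolment to two conditions together: eligibility met or confirmed, and the sheath introduced.
- Appendix A sets the ITT enrolment point, and one limb of the screen-failure definition, at the delivery system rather than the Access Sheath.

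**What follows from enrolment**
- Section 8.8.1 starts adverse event collection at enrolment.
- Section 6.7 lists enrolling a subject who breaches the criteria as a protocol deviation.

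**The concern.** The first echocardiographic exclusion is "Left atrial appendage anatomy cannot accommodate the CLAAS device per manufacturer IFU". The same finding is a natural explanation for an implant attempt that fails. If unsuitable anatomy can be recognised after the sheath is in, and if recognising it means the patient was never enrolled, then membership of the primary analysis population depends partly on how the procedure went.

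Three results would be affected. Device success, procedure success and the primary closure-success endpoint would lose failures from their denominators. The primary safety endpoint would lose any sheath-related event in those patients, and because collection starts at enrolment, the event might not be collected as study data at all. The cap of 20 counts enrolled subjects, so a patient called not enrolled could in effect be replaced, although section 6.6.1 bars replacement of subjects who withdraw. Section 4.3 says the data are to inform a pivotal trial.

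**Working it through.** The plan has no figure to reproduce: section 10.1 gives 20 subjects without a rate, precision target or formula, and there is no hypothesis test. The check is a comparison of rules, followed by an illustration.

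**Step 1. Can the situation arise?** Section 4.2.4.2 says the access sheath "is initially placed into the proper position within the LAA", after which the delivery catheter carries the implant through it. There is therefore an interval with the sheath in and no implant delivered. A check done in that interval satisfies the wording of 7.3.4 and 6.2.2.2.2 but not 7.2 or footnote 12. Even if the check is done before the sheath, unsuitability may first be recognised in that interval.

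**Step 2. How is that patient classified?**

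| Rule | Result for a patient found unsuitable with the sheath in |
|---|---|
| 10.2.1 | Enrolled, in the ITT |
| 6.3 | Can be read as not enrolled, because echocardiographic criteria are not met |
| 6.5, 7.3.6 | Can be read as not enrolled, because one of two joint conditions fails |
| 6.5, screen failure | Does not apply; it covers eligible patients without a sheath |
| Appendix A, screen failure, first limb | Does not apply; ineligibility must be found before the index procedure |
| Appendix A, screen failure, second limb | Does not apply if the sheath is part of the delivery system; might apply if delivery system means only the delivery catheter |
| 6.7 | If enrolled, a deviation; removal is not mentioned |

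No sentence ranks these rules.

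**Step 3. Size for closure success.** Inputs: 20 sheath introductions (section 10.1) and k patients found unsuitable after the sheath. The documents give no value for k, so 1 to 4 is an assumed range. All other patients are taken as successes. Counted: (20 − k)/20. Dropped: (20 − k)/(20 − k). Intervals are exact (Clopper-Pearson) 95%, added for scale; the plan does not call for them.

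| k | Counted (10.2.1) | Dropped (6.3 reading) | Difference, points |
|---|---|---|---|
| 1 | 19/20 = 95.0% (75.1 to 99.9) | 19/19 = 100% (82.4 to 100) | 5 |
| 2 | 18/20 = 90.0% (68.3 to 98.8) | 18/18 = 100% (81.5 to 100) | 10 |
| 3 | 17/20 = 85.0% (62.1 to 96.8) | 17/17 = 100% (80.5 to 100) | 15 |
| 4 | 16/20 = 80.0% (56.3 to 94.3) | 16/16 = 100% (79.4 to 100) | 20 |

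With one further failure among the remaining patients, the differences for k = 1 and 2 are 18/19 − 18/20 = 94.7 − 90.0 = 4.7 points and 17/18 − 17/20 = 94.4 − 85.0 = 9.4 points.

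If dropped patients are replaced until 20 are enrolled, the report reads 20/20 = 100%, against 20/21 = 95.2% (k = 1) or 20/22 = 90.9% (k = 2) of all sheath introductions.

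**Step 4. How likely is at least one case?** For an assumed per-patient probability p, this is 1 − (1 − p)^20: 33.2% at p = 2%, 64.2% at 5%, 87.8% at 10%.

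**Step 5. Safety.** The direction depends on who is dropped. If the one dropped patient had the only event, freedom from major adverse events goes from 19/20 = 95.0% to 19/19 = 100%. If the dropped patient had no event and one other patient did, it goes from 19/20 = 95.0% to 18/19 = 94.7%.

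**The case against.** A reader might infer that Version B permits eligibility to be decided after the sheath is in, and so permits failed implants to be relabelled as ineligible and removed. The documents do not support that. Section 7.2 and footnote 12 require confirmation before enrolment, and a check made before the sheath also satisfies 7.3.4. The order of sections points the same way: transseptal access with a commercial system (7.3.3), then confirmation (7.3.4), then the CLAAS sheath (7.3.6). On the ordinary reading, no screen-failure definition covers a patient with the sheath in. Section 6.7 presupposes that ineligible subjects can be enrolled and handles them as deviations; nothing shows that it would push a site to remove them.

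The consequences are also bounded. The study is descriptive, so no pass or fail decision changes. Some trace would remain: section 6.3 requires a log of screened and consented patients, and section 13.0 records introduced delivery systems on the case report form. The schedule marks adverse events from screening onward, so loss of events is possible rather than certain. An ITT patient without an implant already fails device success, and therefore closure success, by definition.

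All of this stands, and it rules out the stronger reading. It does not remove the conflict. A trace on a log does not fix a denominator, and the rule that non-implanted patients count as failures helps only once they are known to be in the ITT. That is the question left open.

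**Conclusion.** The concern holds as an inconsistency. Version B states the eligibility time point in two ways and the condition for enrolment in two ways, and it leaves unresolved the status of a patient first found unsuitable after the Access Sheath is in. It does not direct that such patients be dropped, and section 10.2.1 taken alone keeps them.

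Under the other reading, each such patient among 20 would raise closure success by about 5 percentage points: from 95% to 100% with one and from 90% to 100% with two. These sizes rest on an assumed number of cases and on no, or one, other failure. In the simplest case the ITT result would also coincide with the Implanted Patient result, so the primary analysis would no longer show what happened to everyone in whom the procedure was begun. That is enough to warrant correction, since the rule in question sets the primary-analysis denominator.

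**What to change.** 1. Reconcile the eligibility time point in 7.3.4, and the matching phrase in 6.2.2.2.2, with 7.2 and footnote 12, so that one time point applies throughout.
2. State in 6.3, 6.5, 7.3.6 and 10.2.1 that every patient in whom the Access Sheath is introduced is enrolled and stays in the ITT whatever is found later, and that ineligibility found later is recorded as a deviation under 6.7.
3. Align the Appendix A definitions of the ITT population and screen failure with the Access Sheath.
4. State that any fit check after the sheath and before deployment is a procedural step and does not alter ITT membership.

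No separate rule for counting non-implanted ITT patients as failures is needed. The cost is wording only; the schedule already calls for ICE before enrolment, so no procedure is added. The reported success rate may be slightly less favourable.

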### 7.3.5 Procedural Imaging

ICE is the primary imaging source before, during, and after CLAAS Implant deployment.

At any time during the study, echocardiographic imaging obtained during a repeat procedure or for diagnostic purposes should also be forwarded to Conformal.

### 7.3.6 CLAAS Implant Deployment

After eligibility has been confirmed and the CLAAS Access Sheath has been introduced into the patient's body, the patient is enrolled in the study and should undergo implantation of the CLAAS Implant per the device Instructions for Use.

Procedural details should be entered into the eCRF. ACT should be measured at the onset of the procedure and at regular intervals throughout the procedure per routine hospital practice.

The procedure is considered complete once the last venous access sheath is removed or the patient has been discharged from the cath lab, whichever is first.

